6.2 Sampling

Study participants will be members of the public from the UK who wish to take part in the online survey. REDCap will be used to ensure balanced randomisation to the framing statements.

6.3 Analysis of Endpoints

The study team will collect data on people's preferences regarding data sharing using Likertstyle scales, yielding interval/ordinal data on preferences (e.g. "very unlikely to share"/"strongly disagree" through to "very likely to share"). For part of the survey, the team will superimpose a randomised intervention, namely a framing statement, prior to seeking views relating to the sharing of mental versus physical health data. The framing statement will be one of three: a "security" framing emphasising previous work reporting others' greater concerns about sharing mental health data versus other kinds of health data; a "neutral" statement; and a "holistic" framing emphasising the interrelationship between mental and physical illness.

The team will examine the distribution of response data and anticipate using general linear modelling when its assumptions are satisfied (e.g. normally distributed residuals) ²⁸ but non-parametric alternatives (e.g. Kruskall-Wallis H test) where they are not. They will use R ²⁶ for statistical analysis. Predictors to be examined include age range, gender, ethnicity, self-reported educational level, geographical indicators (NHS region of respondent, index of multiple deprivation), personal experience of relevant NHS services/disorders, and experimental manipulation (framing).

Primary measures will be the self-reported overall degree of support for: (a) sharing physical health data for NHS clinical care without explicit consent each time, and how far such sharing should extend; (b) likewise for mental health data; (c) sharing de-identified structured physical health data for research without explicit consent, and how far such sharing should extend (e.g. NHS, academic, charities, industry, publicly); (d) likewise for mental health data; (e) as for (c) but with de-identified free text data; (f) as for (d) but with de-identified free text data.

Secondary measures will include (g) the effect of the framing interventions; (h) the degree of support for a single national sign-up mechanism for sharing one's health data for clinical care

and/or research; (i) views on a prototype national NHS data sharing consent form; (j) views on trusted-third-party linkage between health data and a range of other UK state-held data sources (e.g. education, criminal justice).

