An NHS psychological therapy service, e.g. IAPT or other		
therapy service (ONLINE)		
NHS outpatient or community mental health services, or key		
worker		
NHS crisis care/Home Treatment teams		
NHS inpatient mental health services in a mental health		
hospital		
NHS inpatient mental health services in a general hospital		
(liaison psychiatry)		
Private services		
Services in the workplace e.g. Occupational Health		
Charity providing mental health support		
Online forum		
Other (Please specify)		
01	· ·	•

Q4

We are also interested to know if you have accessed any services regarding your own physical health. This could be services like your GP, outpatient hospital appointments, inpatient services, online support, Accident and Emergency, 111 service, private services, charities providing physical health support, etc.

Have you ever used any of the following services for your own physical health?

- I prefer not to say [Will take you straight to Q5]
- I have used physical health services (this includes using your GP)
- I have not used any physical health services [Will take you straight to Q5]

Q4a

And finally, in this section, we would like to know if you would be willing to share what physical health services you have used for your own physical health. You may tick as many boxes as you wish.

Please use the 'next page' button if you prefer not to answer.

Services used	Recently (in the	More than 5
	last 5 years)	years ago
Physical health support from your GP or surgery		
NHS hospital outpatient services (outpatient clinics etc.)		
NHS Urgent Care Centre (not A&E) or NHS 111 helpline		
NHS Accident and Emergency services (A&E)		
NHS inpatient services (procedures not completed in 1 day)		
NHS Day Surgery/day care in a hospital		
Private services		
Services in the workplace e.g. Occupational Health		

Charity providing mental health support	
Online forum	
Other (Please specify)	

Moving on...

The table below shows what NHS identifiable health data may look like. This sort of data is used for health care by NHS staff. (Please note the examples shown are not real).

NHS number	Title	Forename	Surname	Date of birth	Address	Diagnoses	Notes
9876543210	[name]	20 Jan 1950	1 The Street, Maidstone	pneumonia high blood pressure	1 Apr 2019. Seen in clinic. [name] has a fever and a cough. His chest sounds crackly. I think he has pneumonia. Sent to hospital.

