8765432109	Miss	Alice	Jones	16 Jun 1994	15 The Road, Dundee	depression carpal tunnel syndrome	2 Apr 2019. Alice's rates her mood as 1/10 on average, she is more tired, and she is not looking forward to anything. Her depression has worsened. She wishes to restart citalopram.
7654321098	[name]	4 May 1930	5 Tree Close, Cardiff	broken humerus anxiety	3 Apr 2019. Chloe fell after skidding on an oily patch while cycling and was hit by a car. Has an obvious fracture of her left upper arm. Needs X-ray.
6543210987	[name]	22 Sep 1973	27 The Mews, London	schizophrenia diabetes	4 Apr 2019. Pradeep still worries that other people can hear his thoughts, but this is getting less common. He is attending cognitive-behavioural therapy sessions.

[Participants will now randomised to see one of the following three framing questions]

Previous surveys have found that people have more concerns about the use of their identifiable health data relating to their mental health than other aspects of their physical health care.

or

We would like to find out your perspective on using information about your mental health and your physical health.

or

Mental and physical illnesses overlap, so holistic health care is important. Mental health problems have physical consequences, and physical illnesses have important consequences for mental health.

Q5
Regardless of whether you have a physical health condition or have used physical health services:

How likely are you to agree to share your identifiable PHYSICAL health data for your clinical care with the following, without being asked every time?

Sharing Physical Health Data	Very Likely	Likely	Not Sure	Unlikely	Very Unlikely	Prefer not to say
Between my local NHS services i.e. between my local physical and mental health hospitals, my GP, etc.						
Any part of the NHS in my region (cluster of hospitals nearest to my local hospital)						
Any part of the NHS in my home nation only (i.e. only in England, or only in Northern Ireland, or only in Scotland, or only in Wales)						
Any part of the NHS in the UK						

Q6

Regardless of whether you have a mental health condition or have used mental health services:

How likely are you to agree to share your identifiable MENTAL health data for your clinical care with the following, without being asked every time?

Sharing Mental Health Data	Very	Likely	Not	Unlikely	Very	Prefer
	Likely		Sure		Unlikely	not to
						say
Between my local NHS services i.e.						

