	Very Likely	Likely	Not Sure	Unlikely	Very Unlikely	Prefer not to
	- /				/	say
Overall likelihood that you would sign						
up						

The last part of the survey (before we ask a few questions to ensure we have reached a broad section of the UK) examines what a consent form to share our health data could look like. By completing one consent form it would then be possible for all UK NHS professionals to access their patient's identifiable health data for their clinical care, saving time for both patients and health care professionals.

Please take a look at the consent form below:

Q15

Having looked at the consent form, please agree or disagree with the following statements.

(If you would like to take another look at the consent form at any time while answering this question, you can use the 'previous' button at the bottom of this page to look back. This will not affect answers already given.)

	Strongly Agree	Agree	Neither Agree nor Disagree	Disagree	Strongly Disagree	Prefer not to say
The consent form is easy to read.						
The consent form is clear and easy to						
understand.						
The statements (in blue) help me to						
understand what I am consenting to.						
The consent form is clear that my						
identifiable health data would only be						
used by appropriate NHS health care						
professionals.						
I understand the term 'NHS-approved						
researchers' and which individuals this						
may refer to.						
The consent form makes clear that it						
would be used for my preferences						
about sharing my IDENTIFIABLE health						
data within the NHS for my CLINICAL						
CARE.						
The consent form makes clear that it						
would also be used for my preferences						
about sharing my DE-IDENTIFIED health						
data for RESEARCH purposes.						
I would like the consent form to give						
specific options about how researchers						
can contact me (e.g. by post only, e-						
mail).						
I would like to see a statement added						
about the security of data sharing.						
I would like to see a statement added						
about where my consent preferences						
will be stored.						
Before seeing this consent form, I was						
aware of the NHS National Data Opt-						
Out.						
The consent form reassures me that my						
identifiable health data is safe in the						
NHS.						
If this consent form were put in front of						
me today, I would sign it.						

If you would like to make any comments about the consent form, please do so here:

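### The home-nation row in survey Q5 and Q6 keeps a single-choice 'only', so its place between region and UK is ambiguous in the extent part of primary measures (a) and (b)

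*Protocol*

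**What the plan says.** Section 6.3 introduces the endpoints with "Primary measures will be the self-reported overall degree of support for" six items, (a) to (f). Measure (a) is "sharing physical health data for NHS clinical care without explicit consent each time, and how far such sharing should extend", and (b) is the same for mental health data. For the de-identified research measures, reach is a matter of recipient type: "how far such sharing should extend (e.g. NHS, academic, charities, industry, publicly".

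In the Appendix 3 survey, Q5 serves (a) with the stem "How likely are you to agree to share your identifiable PHYSICAL health data for your clinical care with the following, without being asked every time". Q6 serves (b) with "How likely are you to agree to share your identifiable MENTAL health data for your clinical care with the following, without being asked every time". Each stem heads a grid of four areas, and every row is rated from very likely to very unlikely, or prefer not to say. The third row in both grids begins "Any part of the NHS in my home nation only" and goes on to list the four nations, each again with 'only'.

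The introduction to survey Q4 mentions "charities providing physical health support" among the physical health services, but the Q4a table beneath it lists a charity for mental health. The one row in the survey grids labelled as an overall rating is in Q14, "Overall likelihood that you would sign", and it concerns joining a consent system.

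**The concern.** Reach is part of primary measures (a) and (b). To read it from a grid, the rows should nest: whoever accepts UK-wide sharing should also accept sharing within the home nation, the region and locally. The local, region and UK rows do nest. The home-nation row can be read in two ways:

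- **Nested:** I would let any part of my nation's NHS have the data.
- **Restrictive:** I would want sharing to stop at my nation's border.

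Under the second reading, the people most willing to share give that row their lowest rating. A report of support by area could then show a drop at the home nation and a recovery at the UK, caused by wording alone. A larger sample does not reduce this kind of error.

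Two smaller mismatches sit nearby. Q4a records use of a mental health charity in a table about physical health services. Section 6.3 calls the primary measures self-reported overall support, although the grids contain no such rating.

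**Working it through.** **1. The plan's own figure.** Section 6.1 gives three groups, f = 0.1, power 0.9 and n = 1,269. It states no alpha, so 0.05 is assumed. For a one-way ANOVA with noncentrality N × f² = 1,269 × 0.01 = 12.69, power is 0.9001, and 1,269 is the smallest N that reaches 0.9. The figure is reproduced, and nothing below changes it.

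**2. Measures against items (section 6.3 and Appendix 3).**

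| Measure | Survey item | Rated rows | Overall row |
|---|---|---|---|
| (a) | Q5 | 4 | none |
| (b) | Q6 | 4 | none |
| (c) | Q7 | 6 | none |
| (d) | Q8 | 6 | none |
| (e) | Q9 | 6 | none |
| (f) | Q10 | 6 | none |

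Total: 4 + 4 + 6 + 6 + 6 + 6 = 32 rated rows for six measures, with no overall rating. Q14 belongs to secondary measure (h).

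**3. Survey Q2 beside Q5 and Q6.** In Q2 the respondent ticks one of several mutually exclusive choices, so 'only' correctly marks a ceiling. It appears there in both the home-nation and the local options. In Q5 and Q6 each area is rated separately. The local row no longer carries the restriction, but the home-nation row still does. It is the only row of the four that can be read as a ceiling.

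**4. Size, as an illustration.** The documents do not say how respondents read the row, so all inputs here are assumed. Score very likely as 5 and very unlikely as 1. Take a UK-wide supporter who gives 5 to the local, region and UK rows. Let q be the share of such supporters who read row 3 restrictively.

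- Row-3 mean = 5(1 − q) + 1q = 5 − 4q
- Four-row mean = (15 + row-3 mean) / 4

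| q | Row-3 mean | Four-row mean |
|---|---|---|
| 0 | 5.0 | 5.00 |
| 10% | 4.6 | 4.90 |
| 25% | 4.0 | 4.75 |
| 50% | 3.0 | 4.50 |

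The neighbouring region and UK rows stay at 5.0, so the whole dip is an artefact. If UK-wide supporters are a share s of the sample, the full-sample row mean falls by 4 × s × q. The documents give no value for s.

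**5. Where it lands.** The wording is the same in Q5 and Q6, so a respondent who reads it the same way twice shifts both ratings, and a mental-versus-physical contrast partly cancels the shift. The framing statement is randomised, so the mix of readings should be similar across arms. The gradient by area has no such protection.

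**6. Choice of summary.** Take an assumed respondent to one of the six-row grids who scores 5, 5, 4, 3, 1, 1. The mean is 19/6 = 3.2, the maximum 5 and the minimum 1. What counts as overall support therefore depends on the rule chosen.

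**The case against.** A reader might infer that the primary measures cannot be computed. The documents do not support that. Support is self-reported row by row for all of (a) to (f), and the recipient rows of Q7-Q10 follow the kinds of recipient that section 6.3 lists. A scoring rule may stand in a statistical analysis plan that is not shown, so neither its absence nor a choice made after seeing the data can be presumed. What remains is narrower: a score built from rows is derived, whereas section 6.3 describes a self-reported overall rating that the questionnaire never requests.

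A reader might also infer that reach cannot be ordered at all. That too goes too far. The wording touches one row of four in two grids and none in Q7-Q10. The local, region and UK rows keep their order, and the stem lets the third row be read simply as naming an area. Survey Q2 also records reach as one ordered choice. It does not replace (a) and (b), because it does not separate physical from mental data.

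On Q4a, it is fair to say that the effect is small. It is one row of eleven, a free-text 'other' row is available, and the predictor named in section 6.3 is experience of NHS services and disorders, which a charity is not. The label still contradicts its own introduction.

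**Conclusion.** The third row of survey Q5 and Q6 is worded wrongly for a grid. Its place between region and UK is ambiguous, and among UK-wide supporters any restrictive reading can only lower it. In the assumed illustration their row mean falls from 5.0 to 4.6, 4.0 or 3.0 when 10%, 25% or 50% read it that way; the true share is unknown. The damage is mainly to the descriptive extent gradient in (a) and (b). The framing comparison is likely to be little affected, and the mental-versus-physical contrast partly protected, provided that readings are similar across arms and consistent between the two grids. The Q4a label is a plain slip of small consequence. The wording of section 6.3 on overall support is a lesser mismatch with the instrument. The sample size stands.

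**What to change.** 1. In row 3 of survey Q5 and Q6, delete 'only' and the bracketed list of nations, so that the four rows nest. Leave survey Q2 as it is.
2. Appendix 3 gives a link to a live survey. If responses already exist, do not mix two wordings. Keep the row as collected, report it with a note on its ambiguity, and leave it out of any ordered extent score, using the local, region and UK rows.
3. In Q4a, change 'mental' to 'physical' in the charity row, to match the Q4 introduction. If data are already in, do not treat that row as physical health service use.
4. In section 6.3, describe (a) to (f) as derived from the rows of Q5-Q10, either as named rows or as a stated composite, fixed before data are seen. Keep the extent component, so that naming a row does not drop it.

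Before launch, the cost is a few words in the survey and a sentence in section 6.3, with no added items. After launch, it is one usable step fewer in the clinical-care gradient.

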7. ETHICAL AND REGULATORY COMPLIANCE

7.1 Data Protection and Patient Confidentiality

No mandatory personal data is being collected in the survey. However, participants have the option to leave an e-mail address (in order to receive the results of the study) and a further option to leave their postcode. The survey makes clear to participants this will not be used to identify them, but so that results can be analysed by geographic indicators, such as urban versus rural areas and the Index of Multiple Deprivation (IMD) or equivalent outside England.

Participants who choose to leave e-mail addresses will have these removed from the survey data once the survey is closed (but before analysis) and stored on password-protected computers at the University of Cambridge. Access to these e-mail addresses will be by the study team only and will only be used to send out results of the study. Once the initial results have been sent out, the participant will be asked if they would like further updates on the study (publications, abstracts, posters etc) or for their e-mail address to be deleted. Participants will be given 4 weeks to reply with their preference, including 1 reminder email, and if no further correspondence is received the e-mail address will be deleted. Once the likelihood of further results being available is minimal, those participants whose email addresses are still being held will be sent a final email informing them there will be no further results and that their e-mail address will be deleted.

At the same time (once the survey is closed but before analysis) any postcodes given will be converted to a Lower Layer Super Output Area (LSOA) code and the postcode will then be deleted, thus deidentifying all of the data. LSOAs are a geographic division designed to improve the reporting of small area statistics and have been automatically generated from Census data to be as consistent in population size as possible ²⁵. The minimum population is 1000 and the mean is 1500. Postcodes from Scotland and Northern Ireland will be converted to similar geographical areas (Data Zone in Scotland, Super Output Area in Northern Ireland)

and adjusted for IMD ²⁹. If the team are unable to identify an appropriate de-identifiable geographical area, the team will just delete the postcode.

All survey data (now deidentified) will be analysed on University of Cambridge passwordprotected computers. Once the analysis has been finished the fully de-identified data will be available to the public as per the Concordat on Open Research Data ²⁷.

All investigators and study personnel will comply with the requirements of the Data Protection Act ³ with regards to the collection, storage, processing and disclosure of personal information and will uphold the Act's core principles. The Chief Investigator of the study will act as custodian of the data.

7.2 Indemnity

The trial is jointly sponsored by the Cambridge and Peterborough NHS Foundation Trust (CPFT) and the University of Cambridge.

CPFT will accept full financial liability for harm caused to participants in the clinical trial caused through the negligence of its employees and honorary contract holders. There are no specific arrangements for compensation should a participant be harmed through participation in the trial, where no-one has acted negligently.

The University of Cambridge is providing insurance for the study. The University Insurance Manager has advised that insurance for negligent and non-negligent harm under the University's Clinical Trials policy has been arranged. The University's insurers are xxxxx, the insurance policy reference is xxxxx and the Limit of Indemnity under the policy is xxx

8 DISSEMINATION POLICY

The data generated from the survey will be owned by the Chief Investigator for the study. On completion of the study the data will be analysed, and a final study report will be prepared. The study report (and associated documents) will be accessible on the CLIMB project teams website (www.climbproject.org.uk) and the University of Cambridge, Department of

Psychiatry web pages (https://www.psychiatry.cam.ac.uk/). Findings will also be published in journals and at meetings and conferences.

The study team will share the results of the survey with a team at Edinburgh University, who were also successful in being awarded MRC Mental Health Data Pathfinder funding. The Edinburgh team are planning a related but non-overlapping survey on NHS use and health data, and it is hoped that both survey results can be combined to produce some recommendations about sharing health data across the UK.

Participants who choose to leave an e-mail address will be sent a copy of the final report as discussed in the information sheet for the study. Full details of how the study team will do this are in section 7.1 of this protocol. Participants also have the option to receive a copy of any further papers etc. after the results have been published. It is made clear in the information sheet where results can be found for those who do not wish to leave an e-mail address.

The study team will acknowledge the following in their publications: MRC (funders of the mental health data pathfinder award), NIHR. The study team are affiliated to the University of Cambridge and to CPFT.

Once the analysis has been finished the fully de-identified data will be available to the public as per the Concordat on Open Research Data ²⁷ through the University of Cambridge Research Data Repository (https://www.data.cam.ac.uk/repository). This is made clear to participants in the information sheet at the start of the consent survey.

- 30 PA Harris, R Taylor, R Thielke, J Payne, N Gonzalez, JG. Conde, Research electronic data capture (REDCap) A metadata-driven methodology and workflow process for providing translational research informatics support, J Biomed Inform. 2009 Apr;42(2):377-81.

10 Appendices

Appendix 3

Survey

The live survey can be found at:

https://www.redcap-ide-cam.org.uk/surveys/?s=NKTYE8JHCT

or accessed through the project team's website: https://www.climbproject.org.uk/

Actual Survey

Before starting we would like to know where you heard about our study. This is particularly important if you were given information by a GP practice, Hospital or other member of staff. You may prefer not to say if you wish.

• Prefer not to say

• GP (via a poster, leaflet, or from a staff member) [If ticked an option to include GP surgery name will appear]

• Hospital (via a poster, leaflet, or from a staff member) [If ticked an option to include a hospital trust will appear]

- Another health care professional
- Group to which I belong
- Charity website/email/newsletter etc.
- Social media
- Poster (other than at your GP or hospital)
- Browsing the internet
- Friend
- Not sure
- Other (Please specify)

Please read the following definitions:

- By "NHS" we mean all parts of the national health service in the UK: NHS England, NHS Scotland, NHS Wales, and Health and Social Care in Northern Ireland (HSC) and referred to as NHS in this survey
- Health data means any information about a person's health such as might be collected by a nurse, doctor or other appropriate member of NHS staff. Health data includes things like your medical notes, blood test results, prescription information, scans etc.
- Identifiable health data means any health data (as described above) that can also identify a person e.g. any health data that also contains names, addresses, NHS numbers etc.

• Clinical care means providing health care directly to people, for example, diagnosing illnesses or treating ill health

Q1.

We would like to know/gauge your understanding of how NHS clinical care providers currently share your identifiable health data for your clinical care, without asking you each time. If you are not sure, please have a 'best guess' as to what you think might happen.

My understanding is that (please tick only one):

- My identifiable health data is currently shared freely between all NHS sites across the UK-i.e. all acute hospital Trusts, my GP, all mental health Trusts, ambulance service etc. in the whole UK
- My identifiable health data is currently shared between all NHS sites but only in the home nation that I live in -- i.e. shared only in England, or Scotland, or Northern Ireland, or Wales, but not between them
- My identifiable health data is currently only shared between all NHS sites in my region (cluster of hospitals nearest to your local hospital)
- My identifiable health data is currently only shared between my GP, acute local hospital, local mental health Trust and other local services
- My identifiable health data is currently not shared between any NHS sites

Q2.

MOST hospital Trusts, GPs, mental health Trusts are separate and currently DO NOT share identifiable health data without asking you, though they correspond and communicate with each other with your permission.

In view of the statement above, we would now like to ask you your views on sharing your own identifiable health data for YOUR CLINICAL CARE, without having to be asked each time (please tick only one):

- I would like my identifiable health data to be shared for clinical purposes with any part of the NHS in the UK, without asking me first
- I would like my identifiable health data to be shared for clinical purposes with any part of the NHS in my home nation only (i.e. only in England, or only in Northern Ireland, or only in Scotland, or only in Wales) without asking me first
- I would like my identifiable health data to be shared for clinical purposes with any part of my region (cluster of hospitals nearest to your local hospital), without asking me first
- I would like my identifiable health data to be shared for clinical purposes only with my GP, local hospital, and local mental health services, without asking me first
- No one in the NHS should share my identifiable health data without asking me first
- Not sure

We would now like to ask you some questions about your own PHYSICAL and MENTAL health. You can 'prefer not to say' if you wish.

Q3

We would like to ask if you have had a mental health condition either recently or at some point in your life. By mental health conditions we include things like delirium, self-harm, substance abuse,

dementia, mania, schizophrenia, depression, anxiety disorders, psychosis, eating disorders, OCD, personality disorders, etc.

- I prefer not to say [Will take you straight to Q4]
- Yes, I have had a mental health condition either recently or at some point in my lifetime
- No, I have never had a mental health condition [Will take you straight to Q4)

Q3a

We would like to know if you would be willing to share what mental health condition you have had. You may tick as many boxes as you wish.

If you prefer not to say, please use the "next page" button below to move on.

Condition	Recently (in the	More than 5
	last 5 years)	years ago
Delirium		
Alcohol or substance abuse		
Schizophrenia, schizoaffective disorder, or delusional disorder		
Dementia		
Mania or bipolar affective disorder		
Depression		
Anxiety disorder (e.g. phobia, panic, generalized anxiety		
disorder, post-traumatic stress disorder)		
Psychosis of any cause		
Eating disorder (e.g. anorexia nervosa, bulimia)		
Obsessive-compulsive disorder		
Personality disorder		
Self harm		
Other (Please specify)		

Q3b

And also, in relation to mental health. We would also like to know if you have accessed any mental health services for your own mental health condition. These might include your GP, online services, mental health forums, psychological therapy services, crisis care, home treatments or visits, outpatient or inpatient care, services from the private sector, support from a mental health charity, etc.

- I prefer not to say [Will take you straight to Q4]
- I have used mental health services
- I have not used any mental health services (not even my GP or surgery) for my mental health condition [Will take you straight to Q4]

Q3c

We would like to know if you would be willing to share what mental health services you have used for your own mental health condition. You may tick as many boxes as you wish.

Please use the 'next page' button if you prefer not to answer.

Services used	Recently (in the	More than 5
	last 5 years)	years ago
Mental health support from your GP or surgery		
An NHS psychological therapy service, e.g. IAPT or other		
therapy service (INDIVIDUAL session)		
An NHS psychological therapy service, e.g. IAPT or other		
therapy service (GROUP session)		
An NHS psychological therapy service, e.g. IAPT or other		
therapy service (ONLINE)		
NHS outpatient or community mental health services, or key		
worker		
NHS crisis care/Home Treatment teams		
NHS inpatient mental health services in a mental health		
hospital		
NHS inpatient mental health services in a general hospital		
(liaison psychiatry)		
Private services		
Services in the workplace e.g. Occupational Health		
Charity providing mental health support		
Online forum		
Other (Please specify)		
01	· ·	•

Q4

We are also interested to know if you have accessed any services regarding your own physical health. This could be services like your GP, outpatient hospital appointments, inpatient services, online support, Accident and Emergency, 111 service, private services, charities providing physical health support, etc.

Have you ever used any of the following services for your own physical health?

- I prefer not to say [Will take you straight to Q5]
- I have used physical health services (this includes using your GP)
- I have not used any physical health services [Will take you straight to Q5]

Q4a

And finally, in this section, we would like to know if you would be willing to share what physical health services you have used for your own physical health. You may tick as many boxes as you wish.

Please use the 'next page' button if you prefer not to answer.

Services used	Recently (in the	More than 5
	last 5 years)	years ago
Physical health support from your GP or surgery		
NHS hospital outpatient services (outpatient clinics etc.)		
NHS Urgent Care Centre (not A&E) or NHS 111 helpline		
NHS Accident and Emergency services (A&E)		
NHS inpatient services (procedures not completed in 1 day)		
NHS Day Surgery/day care in a hospital		
Private services		
Services in the workplace e.g. Occupational Health		

Charity providing mental health support	
Online forum	
Other (Please specify)	

Moving on...

The table below shows what NHS identifiable health data may look like. This sort of data is used for health care by NHS staff. (Please note the examples shown are not real).

NHS number	Title	Forename	Surname	Date of birth	Address	Diagnoses	Notes
9876543210	[name]	20 Jan 1950	1 The Street, Maidstone	pneumonia high blood pressure	1 Apr 2019. Seen in clinic. [name] has a fever and a cough. His chest sounds crackly. I think he has pneumonia. Sent to hospital.
8765432109	Miss	Alice	Jones	16 Jun 1994	15 The Road, Dundee	depression carpal tunnel syndrome	2 Apr 2019. Alice's rates her mood as 1/10 on average, she is more tired, and she is not looking forward to anything. Her depression has worsened. She wishes to restart citalopram.
7654321098	[name]	4 May 1930	5 Tree Close, Cardiff	broken humerus anxiety	3 Apr 2019. Chloe fell after skidding on an oily patch while cycling and was hit by a car. Has an obvious fracture of her left upper arm. Needs X-ray.
6543210987	[name]	22 Sep 1973	27 The Mews, London	schizophrenia diabetes	4 Apr 2019. Pradeep still worries that other people can hear his thoughts, but this is getting less common. He is attending cognitive-behavioural therapy sessions.

[Participants will now randomised to see one of the following three framing questions]

Previous surveys have found that people have more concerns about the use of their identifiable health data relating to their mental health than other aspects of their physical health care.

or

We would like to find out your perspective on using information about your mental health and your physical health.

or

Mental and physical illnesses overlap, so holistic health care is important. Mental health problems have physical consequences, and physical illnesses have important consequences for mental health.

Q5
Regardless of whether you have a physical health condition or have used physical health services:

How likely are you to agree to share your identifiable PHYSICAL health data for your clinical care with the following, without being asked every time?

Sharing Physical Health Data	Very Likely	Likely	Not Sure	Unlikely	Very Unlikely	Prefer not to say
Between my local NHS services i.e. between my local physical and mental health hospitals, my GP, etc.						
Any part of the NHS in my region (cluster of hospitals nearest to my local hospital)						
Any part of the NHS in my home nation only (i.e. only in England, or only in Northern Ireland, or only in Scotland, or only in Wales)						
Any part of the NHS in the UK						

Q6

Regardless of whether you have a mental health condition or have used mental health services:

How likely are you to agree to share your identifiable MENTAL health data for your clinical care with the following, without being asked every time?

Sharing Mental Health Data	Very	Likely	Not	Unlikely	Very	Prefer
	Likely		Sure		Unlikely	not to
						say
Between my local NHS services i.e.						
between my local physical and mental						
health hospitals, my GP, etc.						
Any part of the NHS in my region (cluster						
of hospitals nearest to my local hospital)						
Any part of the NHS in my home nation						
only (i.e. only in England, or only in						
Northern Ireland, or only in Scotland, or						
only in Wales)						
Any part of the NHS in the UK						

In the next two questions we would like to ask you about sharing your NHS data for research purposes. Research is used to improve overall healthcare for everyone.

Firstly, please look at some of the NHS health care data that you saw previously, which has now been de-identified.

Research ID	Age	Sex	Region	Diagnoses
5X62V	69	М	Kent	pneumonia
				high blood pressure
597PT	24	F	Dundee	depression
				carpal tunnel syndrome
8HG7S	89	F	Glamorganshire	broken humerus
				anxiety
BA6A9	45	М	London	schizophrenia
				diabetes

This type of data is often used for health research. The data still relates to individual people, but information that can identify a person has been removed. The data must still be kept securely, as it still contains details about an individual.

Q7

How likely would you be to share your de-identified PHYSICAL health data with the following, without giving consent every time:

Physical health	Very	Likely	Not	Unlikely	Very	Prefer
	Likely		Sure		Unlikely	not to
						say
Any part of the NHS doing research						
Academic institutions doing research						
(e.g. universities)						
A national charity doing research (e.g.						
MIND, Cancer Research UK, British						
Heart Foundation)						
A profit-making company doing						
research into treatments (e.g. a						
pharmaceutical company, health						
technology company)						
A profit-making company doing other						
research (e.g. an insurance company,						
broadband provider)						
Publicly						

Q8

How likely would you be to share your de-identified MENTAL health data with the following, without giving consent every time:

Mental Health	Very Likely	Likely	Not Sure	Unlikely	Very Unlikely	Prefer not to say
Any part of the NHS doing research						
Academic institutions doing research (e.g. universities)						
A national charity doing research (e.g. MIND, Cancer Research UK, British Heart Foundation)						
A profit-making company doing research into treatments (e.g. a pharmaceutical company, health technology company)						
A profit-making company doing other research (e.g. an insurance company, broadband provider) Publicly						

